#### 6.10.1.2. Univariate Covariate Analysis

If in the analysis of primary endpoint by geography, the resulting p-value is  $\leq 0.15$ , then the following baseline characteristics will be examined individually as potential predictors of death or disabling stroke:

- Gender

This document is electronically controlled. Printed copies are considered uncontrolled.

**Confidential**

- Age
- Baseline NYHA
- STS score
- Baseline LVEF
- Hypertension
- Diabetes
- Coronary artery disease
- Prior stroke
- Prior MI
- Prior PCI

### **6.10.1.3. Multivariable Analysis**

Along with geography and treatment-by-geography interaction, any covariates with a 0.20 significance level from the Univariate Covariate Analysis will be included in a Cox proportional hazard model. If this multivariable regression does not result in a significant (level 0.15) geography by treatment interaction after adjustment for these baseline factors, then outcome results will again be considered poolable across geographies. If geography by treatment interaction is still significant (level 0.15) after adjustment for these factors, results will be presented by geography and the clinical significance of these differences will be assessed.

### **6.10.2. Site Poolability Analysis**

If the geographic regions are considered to be poolable, then the Site Poolability Analysis will be performed on all sites, regardless of geography; the geographic regions (US vs. Other) will not be taken into account.

Should, however, the geographic regions US and Other not be considered to be poolable, then for both of these regions a separate site poolability analysis will take place.

#### **6.10.2.1. Pooling of Small Sites**

Sites should contribute to at least 5 treatment and at least 5 control subjects to the AT set. If this is not the case, the site is considered a “small site”; small sites will be ordered by the date of first procedure in the AT set. Starting with the first “small site”, a pseudo-site will be created by adding subjects from successive “small sites”. Once the number of subjects (treatment and control subject together) reaches or exceeds the size of the median enrollment (treatment and control subject together) of the “large sites”, then a second pseudo-site will be created, beginning with the next site not already included in the first pseudo-site. Additional pseudo-sites, if needed, would be created in the same manner.

If the geographic regions (US vs. Other) are considered to be poolable then the pseudo-sites can consist of small sites of both geographic regions. If however the regions are not considered to be poolable, then specific pseudo-sites for both regions need to be created. A separate site poolability analysis will be performed for both regions.

#### **6.10.2.2. Primary Endpoint by Site**

The interaction between site or pseudo-site and treatment on the probability of death or disabling stroke will be compared using a Cox proportional hazard model. This analysis will be performed in the AT set. If the resulting test is significant at the 0.15 level, further exploratory analysis will be conducted. One analysis will implement a random-effects model for the primary endpoint that includes site as a random effect. Another analysis will attempt to identify covariates that may explain treatment effect differences among the sites. Otherwise, the data will be considered to be poolable across study sites.

This document is electronically controlled. Printed copies are considered uncontrolled.

**Confidential**

### 6.10.2.3. Multivariable Analysis

If in the analysis for Primary Endpoint by Site, the resulting test is significant at the 0.15 level, then the covariates significant at the 0.20 level from Univariate Covariate Analysis (6.10.1.2) will be included along with site in a Cox proportional hazard model. If this multivariable regression does not result in a significant (level 0.15) site by treatment interaction after adjustment for these baseline factors, then outcome results will again be considered poolable across study sites. If site by treatment interaction is still significant (level 0.15) after adjustment for these factors, results will be presented by site and the clinical significance of these differences will be assessed.

---

## 7. Additional Analysis

There will be approximately 50 AT subjects from Japan in this study. Once the primary objective demonstrates non-inferiority (either at one of the interim analyses, or at the final analysis), an additional report specifically for these Japanese subjects will be prepared as requested by PMDA, which includes descriptive statistics for the primary endpoint and all secondary endpoints. In addition, poolability analysis (Japan vs. non-Japan data) will be performed.

---

## 8. Validation Requirements

Statistical programming for the analysis datasets, primary endpoint, secondary safety endpoints, and secondary effectiveness endpoints require Level 1 (independent) validation. Other objectives and sub-group analyses require Level 1 (independent) or Level 2 (Peer review) validation.

---

## 1. Version History

Version	Summary of Changes	Author(s)/Title
1.0	
 
Not Applicable, New Document
 
	[name], Principal Statistician

## 2. List of Abbreviations and Definitions of Terms

Abbreviation	Definition
TAVR	Transcatheter Aortic Valve Replacement
SAVR	Surgical Aortic Valve Replacement
TAV	Transcatheter Aortic Valve
TVT-R	Transcatheter Valve Therapies Registry
CMS	Centers for Medicare & Medicaid Services
KCCQ	Kansas City Cardiomyopathy Questionnaire
RDC	Remote Data Capture
TTE	Transthoracic Echocardiography
ICF	Informed Consent Form
MDCT	Multi-Detector Computed Tomography
PCI	Percutaneous Coronary Intervention
DTL	Delegated Task List
eCRFs	Electronic Case Report Forms
SID Number	Subject Identification Number

## 3. Introduction

This Statistical Analysis Plan has been designed to document, before data are analyzed, the rationale for the study design, and the planned analyses that will be included in study reports. This statistical analysis plan is developed based on the Clinical Investigational Plan (CIP) Addendum.

The Medtronic TAVR in Low Risk Patients Trial is a multi-center, prospective, randomized, interventional pre-market trial. The continued access phase of the trial permits the continued use of the TAVR therapy in patients at low surgical risk after the conclusion of the randomized phase and before receiving FDA approval of the IDE.

The continued access trial is a single-arm, non-randomized study. The purpose of this trial is to further evaluate the safety and effectiveness of the Medtronic TAVR System in patients with severe aortic stenosis at low risk for SAVR. Data from the continued access study will be used to additionally support regulatory submissions for the TAVR in Low Risk Patients study in the United States and other regions where applicable.

## 4. Study Objectives

---

The primary objective of the trial is to evaluate the safety and effectiveness of the Medtronic TAVR system as measured by the rate of all-cause mortality or all stroke at 1 year in subjects who have a low predicted risk of operative mortality for SAVR. Annual clinical summaries will report long term follow-up and monitor adverse events (as collected through the TVT Registry (TVT-R) and Centers for Medicare & Medicaid Services (CMS) claims data) through 10 years post implant.

## 5. Investigation Plan

---

The continued access phase of the Low Risk trial is a multi-center, prospective, non-randomized, interventional trial conducted in the United States. The maximum sample size is not expected to exceed 3660 subjects with an attempted implant, this maximum is based on enrollment during the randomized phase of the trial and will be distributed in semi-annual allocations of 732 attempted implants per 6 months. No site will enroll more than 15% of the semi-annual allocation (i.e., no site will implant > 110 subjects during any given allocation period) without prior authorization from Medtronic. Subjects who exit from the trial after implantation will not be replaced.

All enrolled, qualified, and heart team approved low risk subjects will be implanted with the Medtronic Evolut R or Evolut PRO system. Subjects that undergo an attempted implant or are implanted will be followed via TVT-R through 1 year with assessments at pre-, peri- and post-procedure, discharge, 30 days and 1 year. Additional clinical data available from CMS data claims will be reported out to 10 years.

Subjects will be consented for follow-up through 10 years. The enrollment period for this continued access study will be through completion of FDA review for the PMA supplement for

---

the TAVR Low indication; therefore, the estimated total duration of the trial (first subject enrolled to last subject completing his/her last follow-up exam) is estimated to be 12 years.

## 6. Determination of Sample Size

---

The sample size of the continued access phase of the TAVR in Low Risk Patients Trial will be determined based on FDA approval. The sample size is not expected to exceed 3660 attempted implant subjects at up to 61 hospitals in the United States.

This is not a hypothesis-driven study, therefore the sample size for the analysis was not determined by statistical sample size methods.

## 7. Statistical Methods

---

### 7.1. Disposition of Subjects

This trial will utilize an Oracle RDC system for subject tracking that is the property of Medtronic. Electronic records in Oracle RDC will include subject consent, date of heart team approval, date of attempted implant or implant, the name of the implanters and information identifying the devices used. This trial will also utilize the TVT-R database system for data collection through one year follow up for all attempted implant and implanted subjects.

After all one year follow-up is complete, standard of care clinical data available through claims data submitted to CMS will be provided for 2- through 10-year follow-up. ACC/STS will link CMS claims data with subject records in TVT-R. The CMS and TVT-R linked data is provided to Medtronic with adverse event tables for 2- through 10-year follow-up reporting requirements.

Follow-up visits at 30-day and one year are conducted through TVT Registry. The distribution of follow up visits and visit compliance by one year will be summarized including number expected, visit completed, missed visit, deaths, withdrawal, lost to follow-up and visit pending.

When TVT Registry data is merged with CMS for longer-term follow-up only, subjects that are matched between the databases will be included in subject accountability and analysis. CMS data does not have specified follow-up visits and study exit data is not applicable. The number of subjects in the CMS and TVT-R linked data will provide the number of subjects at risk in the cohort and for each specified timepoint (1-year, 2 years, 3 years, through 10-years). The following will be summarized: expected, completed, deaths, and pending.

## 7.2. Analysis Sets

If the subject signs informed consent, meets all inclusion and none of the exclusion criteria, and the Heart Team determines the subject is suitable for the trial, the subject is assigned TAVR and then added to the approved population. Within the approved population the following analysis sets are distinguished:

- **The attempted implant set:** The attempted implant set consists of all Heart Team approved subjects with an attempted implant procedure, defined as when the subject is brought into the procedure room and any of the following have occurred: anesthesia administered, vascular line placed, TEE placed, or any monitoring line placed.
- **The implanted set:** The Implanted set consists of all the attempted implant subjects who are implanted with the Medtronic TAV device.

## 7.3. General Methodology

Descriptive statistics will be used to report study data. For continuous variables (e.g. age), the mean, median, standard deviation, minimum, maximum and interquartile ranges (IQR) will be presented. For categorical variables, the number and percentage of subjects in the category of interest will be presented.

For time to event variables, Kaplan-Meier analyses of event rates at 30 days, 1 year and annually through 10 years will be presented. For these analyses, the time points will correspond to 30 days, 365 days, 730 days, and annually through 10 years (365×3, 365×4, 365×5, etc.) days post implantation respectively. At each time point with data, the product limit estimate of the event, the number of subjects at risk, the number of subjects with events, and the 95% confidence interval will be presented. For subjects without an event, the date of censoring will be the latest date of all follow-up visits, assessments, and events (including death in those endpoints where death is not the endpoint).

## 7.4. Handling of Missing, Unused, and Spurious Data and Dropouts

Every effort will be undertaken to minimize missing data. In time-to-event outcomes drop-outs will be censored at the time of discontinuation, consistent with the Kaplan-Meier approach.

Data from subjects that cannot be analyzed for a specific variable will be displayed as missing in the relevant summary tables. In this manner, all data for a specific variable are accounted for. No statistical techniques will be used to impute missing data.

In the case of partial dates, if only the month and year are known, the event or assessment will be analyzed as if it occurred on the 15th of that month. If only the year is known, the event or assessment will be analyzed as if it occurred on June 30th of that year. These resolutions of partial dates are subject to the restrictions that events must occur no earlier than the procedure date.

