### **One Year (between 335 and 395 days post implant)**

The following data will be collected for subjects at 1 year to capture data points included in the TVT-R data collection forms including:

- Clinical Assessment
- Five meter walk
- KCCQ-12
- 12-lead ECG
- Echocardiogram
- Medications
- NYHA Classification
- Adverse event assessment

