***Medtronic Confidential***

provided to trial personnel trained and delegated to eCRF completion and / or approval per the DTL. The investigator (or approved sub-investigator) will electronically sign the appropriate pages of each eCRF in Oracle RDC.

After all one year follow-up is complete, sites will no longer enter subject data in the TVT-R database. Standard of care clinical data available through claims data submitted to CMS will be provided for 2- through 10-year follow-up. ACC/STS will link CMS claims data with subject records in TVT-R. The CMS and TVT-R linked data is provided to Medtronic with adverse event tables for 2- through 10-year follow-up reporting requirements.

Any clinical data entered in to the databases must have a corresponding source document.

All trial-related documents must be retained until notified by Medtronic that retention is no longer required. Medtronic will inform the investigator/institution when these documents are no longer required to be retained.

No trial document or image should be destroyed without prior written agreement between Medtronic and the investigator. Should the investigator wish to assign the trial records to another party or move them to another location, advance written notice must be given to Medtronic.

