## 7.7. Evaluation of Objectives

### 7.7.1. Primary Endpoint

All-cause Mortality or all Stroke Rate at 1-year post procedure.

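### The continued-access partial-date rule is bounded only by the procedure date, so it can date an event after the form that reported it and move events across day 30 and day 365

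*SAP*

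**What the plan says.** Continued Access SAP 7.4 resolves incomplete dates with two fixed substitutions. When the day is missing, "if only the month and year are known, the event or assessment will be analyzed as if it occurred on the 15th of that month". When the month is missing too, "If only the year is known, the event or assessment will be analyzed as if it occurred on June 30th of that year". One condition follows: "These resolutions of partial dates are subject to the restrictions that events must occur no earlier than the procedure date". Neither the Continued Access SAP nor the addendum caps the resolved date at the reporting form, last contact, death or data cut. The main-trial SAP has no partial-date rule that could fill the gap.

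The resolved dates feed Kaplan-Meier estimates at fixed days. Under Continued Access SAP 7.3, "the time points will correspond to 30 days, 365 days, 730 days, and annually through 10 years". Section 7.7 reports the primary and secondary safety endpoints at 30 days and 12 months; the primary endpoint is "All-cause Mortality or all Stroke Rate at 1-year post procedure".

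Events up to one year come from TVT-R forms (addendum 8.5). The addendum's schedule (8.1) places the 30-day visit at days 30 to 45 and the one-year visit at days 335 to 395. Addendum 8.6 adds: "After all one year follow-up is complete, sites will no longer enter subject data in the TVT-R database".

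**The concern.** An event reported on a form cannot have happened after that form was completed. The form date is therefore an upper limit on any partial date it carries, and the rule does not use it. A mid-year substitute can be far from a date that the procedure and the form already confine to a narrow interval. It can also fall on the wrong side of day 30 or day 365.

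Which way an event moves is set by the calendar month of implant, which has no clinical meaning. At stake is whether affected events are counted in the one-year death-or-stroke rate and in the 30-day safety rates.

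**Working it through.** The plan states no figure to reproduce, so the check applies the written rule by calendar arithmetic.

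**Inputs from the documents:** 30 June and 15th-of-month substitution, with the procedure date as lower bound (Continued Access SAP 7.4); landmarks at days 30 and 365 (7.3); visit windows of days 30–45 and 335–395 (addendum 8.1).

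**Assumptions, not in the documents:** implant dates uniform over a 365-day year; true event days uniform on 0 to 365 unless stated; a date before the procedure is moved to the procedure date. Example years are illustrative.

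1. **Past day 365.** Implant 1 March 2018, true event 20 January 2019 (day 325), recorded as 2019. The one-year window is 30 January to 31 March 2019. The rule gives 30 June 2019, day 486, which is past day 365 and after any in-window form. With implant on 1 March 2019 and an event recorded as 2020, the window closes on 30 March 2020 and the rule gives day 487.

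2. **How often.** There are 365 × 366 = 133,590 pairs of implant date and event day. For the n-th day of the year, n event days fall in the next calendar year. Implants from 1 January to 29 June (n = 1 to 180) give 180 × 181 / 2 = 16,290 pairs, and 16,290 / 133,590 = 12.2%.

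3. **Later than the form.** With the form at day 365, all of these dates are later than the form. With the form at day 395, this holds for implants up to 30 May (n = 1 to 150): 150 × 151 / 2 = 11,325, or 11,325 / 16,290 = 70% of them.

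4. **Before the procedure.** Implant 1 October 2018, true event 20 December 2018 (day 80), recorded as 2018. 30 June 2018 is 93 days before the procedure. If moved to the procedure date, the event is at day 0. Implants from 1 July to 31 December with a same-year event give 184 × 185 / 2 = 17,020 pairs, or 12.7%. Of these, 153 × 154 / 2 = 11,781 pairs (8.8% of all pairs) are truly after day 30.

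5. **Other entries to the 30-day rate.** For implants from 31 May to 30 June, 30 June is itself within 30 days. Same-year events truly after day 30 add 31 × 169 = 5,239 pairs (3.9%). Total wrongly entering: 8.8% + 3.9% = 12.7%.

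6. **Exits from the 30-day rate.** For implants from 1 January to 30 May (150 days), every true 30-day event is dated after day 30. December implants whose event falls in January add the equivalent of (1 + 2 + … + 30) / 31 = 15 days. So (150 + 15) / 365 = 45.2% of year-only events truly within 30 days are moved out.

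7. **Net 30-day effect.** Let q be the share of year-only events truly within 30 days, spread evenly on each side of day 30. The fraction of later events moved in is 0.1274 / (335 / 366) = 0.139.
   - Uniform timing, q = 31 / 366 = 8.5%: 8.5 + 12.7 − 0.452 × 8.5 = 17.4%, a rise.
   - Early-weighted, q = 40%: 40 + 0.139 × 60 − 0.452 × 40 = 30.3%, a fall.
   - No net change at q = 0.139 / (0.139 + 0.452), about 24%.

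8. **Month-only dates.** Implant 10 March 2018, form 5 March 2019 (day 360), event recorded as March 2019. The rule gives 15 March 2019, day 370, which is after the form and past day 365.

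**The case against.** The best defence is that this is a transparent, pre-specified fallback in a single-arm descriptive study with no hypothesis test. Stroke, part of the primary endpoint, is adjudicated by a contracted organisation that may request source documents (addendum 8.5), and TVT-R data pass programmatic checks (13.3). Nothing shows how often a date arrives with only the year. All of this stands. It limits the size of the problem but does not make an impossible date acceptable.

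Some stronger readings are tempting, and the documents do not support them:

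- **That the rule inflates the 30-day rate.** It moves events both ways, and the net direction turns on how early events occur. Entry at day 0 is also an inference, because 7.4 does not say where a date that breaches the bound is placed.
- **That every implant before 30 June yields a date after the reporting form.** Crossing day 365 is general for next-year events, but a form late in its window can postdate 30 June for June implants.
- **That every one-year-form event dated past day 365 is wrongly excluded.** An event truly on days 366 to 395 may properly be on that form and outside the day-365 rate.
- **That an imputed stroke date after death distorts the primary composite.** A dated death is itself a primary event, so this matters only for endpoints such as stroke alone.
- **That the registry already contradicts the imputed dates.** The schedule lists an adverse event assessment at each visit, but the documents do not show that absence of each event is recorded by form or that form dates reach the sponsor.

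**Conclusion.** The point holds as a minor defect in a stated rule. The percentages are shares of year-only events under assumed timing, not shares of all events, and the day-0 figures also need the assumed reset to the procedure date. Because the documents do not give the share of partial dates, no bias in any reported rate can be claimed. The consequence is confined to the descriptive continued-access results.

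**What to change.** Replace the two fixed substitutions in Continued Access SAP 7.4 with one bounded rule:

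- Restrict the date to the known month or year.
- Bound it below by the procedure date or, where the registry data show it, by the last form recording no such event, if later.
- Bound it above by the earliest of the reporting-form date, death and last contact.
- Use the midpoint of the remaining interval.

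In the first example, with the form assumed at day 360 (24 February 2019), the interval is 1 January to 24 February 2019. Its midpoint is 28 January 2019, day 333, so the event stays in the one-year rate. In the October example the interval is days 0 to 91 and the midpoint is day 45 rather than day 0. An upper bound alone would not cure that case. A year-only event reported on a 30-day form, assumed at day 35 after a 1 March implant, would fall at (0 + 35) / 2, about day 18, instead of 30 June.

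The cost is two sentences of SAP text, a few lines of derivation code, and confirmation that form dates are in the TVT-R transfer. If absence by form is not recorded, the procedure date remains the lower bound and the rest of the rule still works.
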